APPENDIX

Instagram Intervention Posts

Image 1.

Caption 1. It can be easy not to be present when you're going through the motions. Next time, try to focus your attention on your breath, and do things with intent.

Image 2.

Caption 2. A lot of people think alcohol helps them fall asleep, but it can actually cause you to wake up throughout the night and get less sleep overall. Have you ever had a drink right before bed? What do you do to make sure you can get a good night's rest?

Image 3.

Caption 3. This definition is brought to you by the National Institute of Alcohol Abuse and Alcoholism. Do you binge-drink?

Image 4.

[figure not shown]
Caption 4. Share how you know it's time to call it a night.

Image 5.

Caption 5. What can you do for yourself today? Sometimes happiness isn't something we find, but it's something we can create!

Image 6.

Caption 6. Homework? Making time for family? Saving extra money? It's important to prioritize the things that matter to you!

Image 7.

Caption 7. Happy Friday! What are you proud of accomplishing this week? What are your goals for next week?

Image 8.

[figure not shown]
Caption 8. In 2016, over 10,000 people died as a result of an accident involving alcohol-impaired driving. What will you do to prevent drunk driving tragedies?

Image 9.

Caption 9. Give yourself a moment this morning to really taste whatever your morning drink is, whether it be coffee, tea, or water. Let yourself savor it. Notice the smell (if there is one), the temperature, the texture.

Image 10.

**CUT BACK ON DRINKING, AND
SAVE MORE MONEY!**

Caption 10. Drinking can put a dent in your bank account. If you cut back on drinking, you might see your savings flourish!

Image 11.

Caption 11. You're the expert on you! You know your limits and what's important to you.

Image 12.

[figure not shown]
Caption 12. Know the signs of alcohol poisoning so that you can keep yourself and your friends safe!

Symptoms include:

- Confusion

- Passing out
- Vomiting
- Seizures
- Slow or irregular breathing
- Slow heart rate
- Clammy skin
- Dulled responses
- Extremely low body temperature

Image 13.

Caption 13. Do you drink more than the average of people your age?

Image 14.

Caption 14. You did it! You made it another week *party emoji* Remember to take some time to reward yourself for powering through! Whether it be a walk or watching your favorite show, no act of self-appreciation is too small.

Image 15.

Caption 15. Some drinks have much higher alcohol content than others. One small shot has the same amount of alcohol on average as a glass of beer or wine. How could you change your drinking so that there is a less chance of you getting sick?

Image 16.

[figure not shown]
Caption 16. Was your answer a zero? If it was another number, why is that? What makes you feel like you're - even a little bit - ready to change your drinking habits? Think about your strengths and past successes that you could draw on.

Image 17.

Caption 17. Taking a moment to notice what's around you is a useful practice whenever you find yourself getting caught up in your thoughts and feelings.

Image 18.

Caption 18. Eating before drinking can help keep you from getting sick. What's your favorite thing to eat when you plan on drinking throughout the night?

[figure not shown]
Image 19.

Hangover Avoidance Tip: Have a glass of water in between every alcoholic drink.

Caption 19. When was the last time you had a really awful hangover? What do you do to avoid them?

Image 20.

Caption 20. Drinking can dehydrate you and kill your complexion. Cutting back can help you get that healthy glow!

Image 21.

[figure not shown]
Caption 21. Another week down! What are you looking forward to this weekend? What are your goals for next week?

Image 22.

Caption 22. Take a moment to reflect on the things that make you happy. Think of three things, and name them below in the comments [finger pointing down emoji]

Image 23.

Caption 23. Feeling too warm, woozy, or a little nauseous? All of these can be a sign that it is time to pause your drinking. How does your body tell you that you've reached your limit?

Image 24.

Caption 24. Craving = feeling the need to drink

[figure not shown]
Loss of Control = drinking more than you planned

Physical dependence = needing a drink to feel okay

Tolerance = having to drink more to feel the effects

Have you ever experienced any of these?

Image 25.

[figure not shown]
Caption 25. Mindfulness is a set of practices that help you to ground yourself by staying the moment. What is your favorite way to stay mindful?

Image 26.

Caption 26. Treat yourself like you would treat your best friend.

Image 27.

Caption 27.

What can you do today (minus drinking) to bring yourself joy?

Image 28.

Caption 28. You did that! Give yourself credit where credit is due. Think about your goals, and go for them!

Image 29.

[figure not shown]
Caption 29. One of the best ways to make sure that everyone stays safe during a night of drinking is sticking with those you know and trust. Write down the name of one person you trust.

Image 30.

Caption 30. Tell us in the comments what you're noticing right now.

Image 31.

Caption 31. It's all about the fun you can have! Keeping your body moving can help you to drink at a safe pace. What's your favorite song to dance to?

Image 32.

Caption 32. Take your time, examine your food, and really taste it. Use intent with each bite so that you can stay in the present and notice how the flavor changes.

Image 33.

Caption 33. Once you have a number in mind, ask yourself: why that number and not zero?

Imagine what you would gain from cutting back on alcohol.

Image 34.

[figure not shown]
Caption 34. Instead of rushing through your drink, take your time to enjoy it!

Image 35.

Caption 35. How do you reward yourself after a tough week? Some quiet time with a good book, a nice long walk, or an impromptu dance break can go a long way!

Image 36.

Caption 36. Having trouble concentrating? Your drinking might be making it worse.

Image 37.

[figure not shown]
Caption 37. One way to make sure you don't end up drinking more than you would like is to set a time ahead of time for when you'd like to stop. How else can you make sure not to drink too much?

Image 38.

Caption 38. Mindful breathing can be a great practice for when you're feeling overwhelmed or disconnected. Take a few moments, and remember this pattern: 4 - 7 -8.

Image 39.

Caption 39. You have the power to prioritize the things that matter to you and to achieve your goals! Put your values first, and the rest will follow.

Image 40.

Caption 40. The people who love you can worry about your safety when you're out. Make sure to get a safe ride home!

Image 41.

Caption 41. Alcohol can impair your body's ability to build muscle, which means that drinking might get in the way of your fitness goals. What's your favorite way to get your body moving?

Image 42.

Caption 42. Reflect on all that you have accomplished this week, even the things that seem small, and celebrate each victory with a little self-care.

This is our last post! Thanks for participating in the project. Please stay followed to us for at least this next week, and keep a lookout for the final survey, which will be emailed to you four weeks from today [insert date]. Take care, and be well!

Story 1.

PROJECT
SNAPSHOT

DID YOU KNOW?

**AN EASY WAY TO CUT BACK
ON DRINKING IS KEEPING
ALCOHOL OFF YOUR
GROCERY LIST.**

The less alcohol you have in your home, the less likely you are to drink. Easy access can lead to drinking more than you'd want.

Story 2.

Story 3.

Quiz included: With options “True” or “False”

Story 4.

PROJECT
SNAPSHOT

Ever find yourself
craving a drink?

Next time, try imagining the
feeling like a wave. Urges to drink
can get really intense before they
start to decline.

Story 5.

**PROJECT
SNAPSHOT**

1 for 1: Water for Alcohol

For every sip of alcohol, take a sip of water. This can help you pace yourself and keep you from drinking more than you would like.

Story 6.

PROJECT
SNAPSHOT

**AN EMPTY STOMACH
CAN CAUSE A
DRINKING DISASTER.**

TRY PAIRING YOUR DRINK WITH
SOME FOOD TO HELP WITH
PACING.

Story 7.

**PROJECT
SNAPSHOT**

Mindful Minute

Take a moment to imagine leaves
flowing down a stream.

Acknowledge each thought you
have, and then, place them on a
leaf, one by one. Visualize the
leaves flowing down the stream.

Story 8.

PROJECT SNAPSHOT

DOES YOUR DRINKING CHANGE BASED ON CONTEXT?

SOMETIMES THE PEOPLE AROUND US AND WHERE WE ARE CAN INFLUENCE THE WAY WE DRINK. PAYING ATTENTION TO THESE PATTERNS HELPS US NOT TO DRINK MORE THAN WE WOULD LIKE.

Story 9.

PROJECT SNAPSHOT

When you have someone who is with you the entire night and can help you keep track of how much your drinking, it can help you from over-drinking.

**Keep trusted friends close by
during a night of drinking!**

Story 10.

Poll included: "Have you ever set a limit on how much you want to drink ahead of time?"

Answers: "Yes" or "No"

Story 11.

Mindful Listening

PROJECT
SNAPSHOT

Take a moment today to listen to your favorite song. Try to listen to it as if it were your first time ever hearing it. What do you notice? What kind of emotions or thoughts come up? How does the music make you feel?

Story 12.

[figure not shown]

**PROJECT
SNAPSHOT**

WHAT IS A STANDARD SERVING
SIZE FOR A GLASS OF WINE?

[figure not shown]
Quiz included: With options “3 oz,” “4 oz,” “5 oz,” or “6 oz”

Story 13.

Quiz included: With options “10 oz,” “12 oz,” “14 oz,” or “16 oz”

Story 14.

Quiz included: With options “1.5 oz,” “2 oz,” “2.5 oz,” or “3 oz”

Story 15.

PROJECT SNAPSHOT

[figure not shown]
Take a mindful walk.

Notice the sights, the sounds, and the way your body moves. Feel the ground beneath you as you walk.

Story 16.

PROJECT
SNAPSHOT

IF YOU'RE WORRIED A
FRIEND MAY BE
SUFFERING FROM

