The intervention was rated as highly acceptable. Additionally, analyses revealed significant within-subjects decreases in past-month alcohol consumption, drinking days, and binge-drinking days post-intervention; however, there were no significant changes in past-month protective behavioral strategies and mindfulness practices. Although this pilot study provided critical feedback about intervention development and administration, it was intentionally small and did not include a control group, thereby limiting the interpretation of findings. The proposed study builds on this pilot work by replicating the study with a larger sample size, a community-based sample, and an assessment-only control group. Specific procedures are described below.

Chapter 2: Methods

Participants

Eighty participants will be recruited from Prolific, an online platform designed to screen and recruit potential research participants for online studies. Power analyses indicate that, with an N of 80 (two groups of 40), this study will be sufficiently powered to detect effect sizes of .20, an effect size consistent with other standalone, technology-delivered, cognitive behavioral interventions for alcohol use (Kiluk et al., 2019).

In order to be eligible for the study, participants must: (1) be a US resident, (2) be between the ages of 18 and 30; (3) report at least two binge-drinking episodes (i.e., four or more drinks in one sitting for cis women, five or more drinks in one sitting for cis men or transgender and

nonbinary individuals) per month over the past three months; (4) have an active Instagram page; and (5) report regular Instagram use (i.e., at least 2-3 times a week).

Participants will be randomized to either an intervention condition in which they will follow an Instagram page and engage with content during the six-week study period or to an assessment-only control condition in which they will be emailed assessment measures, but will not be exposed to intervention content.

Measures

Demographics will be assessed at baseline. Participants will be asked to answer questions about their sex, gender, age, race, ethnicity, sexual orientation, education level, and household income. State of residence will also be assessed.

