prioritize the things that matter to you and to achieve your goals! Put your values first, and the rest will follow”) or prompt participants to reflect on their own individual values and skills (e.g., “You did that! Give yourself credit where credit is due. Think about your goals and go for them!”).

Protective Behavioral Strategies. Protective behavioral strategy posts will reference specific behaviors that can increase or decrease the consequences of alcohol use (e.g., “Drinking games can be dangerous. Drinking too much, especially in short spans, can lead to alcohol poisoning. What was once fun can become frightening.”). Other posts will ask participants to reflect on protective behavioral strategies that they have used in the past or have seen others use effectively.

Procedure

Recruitment and Baseline. Eighty participants will be recruited using a screening survey administered through Prolific, a research recruitment website. Eligible participants will be given access to the main study on Prolific, and those randomized to the intervention condition will be invited to follow the study Instagram page. Before being given the Instagram page username, participants will be asked to agree to the following study guidelines/expectations:

- 1) They will follow the Instagram intervention page for the duration of the 6-week study
- 2) They will treat their fellow group members with respect and avoid “trolling” (i.e., contacting other participants, posting disrespectful comments, using obscene language, etc.)
- 3) They will participate, comment, and share when they feel comfortable doing so
- 4) They will ‘like’ intervention content posts as they appear on their feed (as a way of indicating that they have seen them)

5) While their comments and interactions on the page will not be seen by the general public, other participants will be able to view them and interact with them

After agreeing to these expectations, participants will be asked to provide their Instagram username, sent a baseline survey containing a link to the Instagram page and the baseline questionnaires, and instructed to begin following the Instagram page immediately.

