In order to prevent delays between baseline survey completion and the start of the Instagram intervention, subgroups of participants may be randomized to condition and exposed to the intervention in different data collection waves. Each wave will last for six weeks and will contain a total of forty-two Instagram posts and twenty-one Instagram ‘stories’ (i.e., images that are available for viewing for twenty-four hours after posting and can utilize mechanics like polls and quizzes). Intervention content will be posted once per day throughout the 6-week intervention period, alternating between posting times of approximately 8 AM EST/EDT and 8 PM EST/EDT, and intervention ‘stories’ will be posted once every two days.

10-Week Follow-Up Survey. Ten weeks after the intervention start date (and four weeks after the end of the intervention), participants will be emailed a follow-up survey, which will contain the same questionnaires as the baseline survey. Participants in the intervention condition will also be asked to rate how relevant, respectful, helpful, empathic, personalized, and interesting they felt the intervention content had been, using 5-point Likert scales. Additionally, participants in the intervention group will be shown specific examples of previously posted content and asked to rate each specific post on the dimensions listed above, as well as to indicate whether they remembered seeing those particular posts.

The follow-up survey will remain open for two weeks, and reminder messages will be sent during this time to encourage participant completion. Each participant will receive \$10 for completing the baseline session and \$15 for completing the 10-week online follow-up survey.

Analytic Strategy and Hypotheses

The data will be assessed for normality, missing data, and outliers. Data transformation, multiple imputation, and list-wise deletion will be utilized as needed. Mixed repeated-measure ANOVAs will be used to analyze within- and between-group differences in participants' alcohol consumption, alcohol-related consequences, mindfulness practices, and use of protective behavioral strategies at baseline and 10-week follow-up. Average acceptability ratings will be calculated using group means.

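### The last Instagram post gives intervention participants the final-survey date four weeks ahead; no equivalent notice to controls is described

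*Combined protocol and SAP*

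**What the plan says.** The Appendix (Instagram Intervention Posts) ends with Caption 42. It thanks participants and asks them to "keep a lookout for the final survey, which will be emailed to you four weeks from today", followed by a placeholder for the date.

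The post reaches one arm. Under Procedure, Recruitment and Baseline, "those randomized to the intervention condition will be invited to follow the study Instagram page". Under Participants, the assessment-only controls "will be emailed assessment measures, but will not be exposed to intervention content". The plan describes no contact with controls between the baseline survey and the week-10 email.

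The follow-up procedure (10-Week Follow-Up Survey) is written for participants in general: "Ten weeks after the intervention start date (and four weeks after the end of the intervention), participants will be emailed a follow-up survey". It continues: "The follow-up survey will remain open for two weeks, and reminder messages will be sent during this time to encourage participant completion". Each participant receives $15 "for completing the 10-week online follow-up survey".

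The Analytic Strategy allows data transformation, multiple imputation and list-wise deletion as needed. It gives no rule for choosing among them, no expected attrition rate and no comparison of loss by arm.

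**The concern.** Contact aimed at securing the outcome measurement should be the same in both arms. Here one arm receives a dated prompt four weeks before the survey. The reminders do not offset it: they start only once the survey is open, so they add equally to both arms.

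At stake is the comparability of the people who answer at week 10. The trial has 40 participants per arm and a single follow-up survey. A repeated-measures ANOVA on baseline and week 10 with list-wise deletion drops everyone who does not answer that survey. If response differed by arm and non-responders had changed differently from responders, the group-by-time contrast among completers would be shifted.

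**Working it through.** **Contacts by arm, as described**

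| Contact | Intervention | Control |
|---|---|---|
| Baseline survey, $10 | yes | yes |
| 42 posts and 21 stories over six weeks | yes | no |
| Dated notice of the final survey, end of week 6 (Caption 42) | yes | none described |
| Emailed survey at week 10 | yes | yes |
| Two-week window with reminders | yes | yes |
| $15 for completion | yes | yes |

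The timing is internally consistent: 42 daily posts plus four weeks is 42 + 28 = 70 days, or ten weeks. Caption 42 is therefore a true advance notice of the week-10 survey. It is the only row about securing follow-up that differs by arm. The posts and stories also differ, but they are the intervention itself.

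**Size of a possible bias.** The plan gives no attrition figure, so there is none to reproduce and every rate below is an assumption. Let L_I and L_C be the proportions lost in the intervention and control arms. Let d be the mean change in non-responders minus that in responders, in SD units, taken as equal in both arms.

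- In each arm, completer mean = full mean − L × d.
- Bias in intervention minus control = (L_C − L_I) × d, that is, retention gap × d.

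| Assumed gap | d = 0.25 | d = 0.50 | d = 0.75 |
|---|---|---|---|
| 5 points | 0.0125 | 0.025 | 0.0375 |
| 10 points | 0.025 | 0.05 | 0.075 |
| 15 points | 0.0375 | 0.075 | 0.1125 |

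The range is 0.01 to 0.11 SD. With d = 0 the bias is zero whatever the gap. If the intervention arm loses more, the sign reverses. For example, if non-responders reduce their drinking less and controls are lost more often, the intervention's benefit is understated; if intervention participants are lost more often, it is overstated.

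**Against the planned effect.** Participants gives .20 without a metric.

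- If it is Cohen's d: 0.0125/0.20 = 6% to 0.1125/0.20 = 56%.
- If it is Cohen's f, two groups imply d = 2 × 0.20 = 0.40, and the shares halve to about 3% to 28%.

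**Precision.** A 10-point gap is 0.10 × 40 = 4 participants. With 10% against 20% loss, 36 and 32 complete. Relative to 36 and 36, the standard error grows by √[(1/36 + 1/32)/(2/36)] = 1.03, about 3%. Any harm would come through bias, not lost precision.

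**The case against.** The strongest reply is that Caption 42 is a one-sentence sign-off and that everything that actually collects the outcome is the same in both arms: the email, the window, the reminders and the payment. That stands, and it is why the point is minor.

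A reader might infer that the intervention arm alone knows in advance when the survey is coming. The documents do not establish this. Consent pages are not in the public text and may have told everyone the follow-up date. The Appendix reproduces posts and stories only, with no email wording for either arm, so the lack of a control message there proves little. The supportable statement is that no equivalent notice is described. Even if consent gave everyone the date at entry, the week-6 prompt would remain an extra contact for one arm.

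A reader might also infer that follow-up depends on assigned arm. That states a possibility as fact. The plan contains no attrition data, and the direction is open: intervention participants carry six weeks of extra participation and could be lost more often, in which case the post would narrow the gap.

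Nor do the documents support saying that no analysis could repair unequal loss. Multiple imputation is permitted and is valid if missingness depends only on observed data such as baseline drinking. What is fair is that the plan sets no rule for when imputation or list-wise deletion applies, so the safeguard is not assured.

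**Conclusion.** The point holds as a minor design asymmetry. Followed as written, the plan gives one arm a dated follow-up prompt that is not described for the other. This may contribute to unequal response, in an unknown direction and to an unknown degree.

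The 0.01 to 0.11 SD range is illustrative. It rests on assumed gaps of 5 to 15 points in total retention, on non-responders differing from responders by 0.25 to 0.75 SD equally in both arms, and on a completer analysis. Nothing ties a gap of that size to one post, and retention may differ anyway because an assessment-only control has far less contact. The 6% to 56% share should therefore not be read as the effect of Caption 42, and it applies only if .20 is Cohen's d.

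The change is still worth making: the difference is avoidable, the remedy is almost free, and a bias of unknown sign cannot be corrected reliably afterwards.

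**What to change.** - On the last posting day of each wave, send participants in both arms the same neutral message by the same channel (email or the recruitment platform), giving the survey date and the $15 payment.
- Remove the survey notice from post 42, or keep it only as a duplicate of that message.
- Report follow-up completion and response date by arm. Present completion as a difference with an interval rather than relying on a test: with 40 per arm, a two-sided 5% test has about 24% power for 10% against 20% loss and about 61% for 10% against 30%, so a non-significant result would not be reassuring.

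The cost is one templated message per wave, one caption edit and two lines in the results. The downside is one extra contact with controls, which matches what the other arm already receives. The change does not equalise contact from the intervention content, and it is not meant to.
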